## 4.3 Observational Endpoints and Assessment Methods

### 4.3.1 Safety

The observational safety objective is presented in [Section 2.3.1](#).

#### 4.3.1.1 Safety Definitions

The following definitions are taken from the ICH E2A Guideline for Clinical Safety Data Management: Definitions and Standards for Expedited Reporting.

Adverse Event:

An AE is any untoward medical occurrence in a patient or clinical investigation subject administered a pharmaceutical product and which does not necessarily have to have a causal relationship with this treatment. An AE can therefore be any unfavorable and unintended sign (including an abnormal laboratory finding, for example), symptom or disease temporally associated with the use of a medicinal product, whether or not considered related to the medicinal product.

Therefore an AE may be:

- A new illness
- The worsening of a concomitant illness
- An effect of the vaccination, including the comparator
- A combination of the above

All AEs include serious and non-serious AEs.

Surgical procedures are not AEs; they are the action taken to treat a medical condition. It is the condition leading to the action taken that is the AE (if it occurs during the trial period).

Pre-existing medical conditions are not to be reported as AEs. However, if a pre-existing condition worsens in frequency or intensity, or if in the assessment of the treating physician there is a change in its clinical significance, this change should be reported as an AE (exacerbation). This applies equally to recurring episodes of pre-existing conditions (e.g., asthma) if the frequency or intensity increases post-vaccination.

***Serious Adverse Event:***

*Serious* and *severe* are not synonymous. The term *severe* is often used to describe the intensity of a specific event as corresponding to Grade 3. This is not the same as *serious* which is based on patient/event outcome or action criteria usually associated with events that pose a threat to a patient's life or functioning. Seriousness, not severity, serves as a guide for defining regulatory reporting obligations.

An SAE is any untoward medical occurrence that at any dose

- Results in death
- Is life-threateninga
- Requires inpatient hospitalization or prolongation of existing hospitalizationb
- Results in persistent or significant disability/incapacityc

---

a The term "life-threatening" refers to an event in which the subject was at risk of death at the time of the event; it does not refer to an event which hypothetically might have caused death if it were more severe.

b All medical events leading to hospitalizations will be recorded and reported as SAEs, with the exception of: hospitalization planned before inclusion into the study or outpatient treatment with no hospitalization.

c "Persistent or significant disability or incapacity" means that there is a substantial disruption of a person's ability to carry out normal life functions.

- Is a congenital anomaly/birth defect
- Is an important medical eventa

Additionally, the following important medical events are to be considered as SAEs:

- New onset of Guillain-Barré syndrome (GBS), encephalitis/myelitis (including transverse myelitis), neuritis (including Bell's palsy, optic neuritis, and brachial neuritis), thrombocytopenia, vasculitis, convulsions (including febrile convulsions), and anaphylaxis or other hypersensitivity/allergic reactions

***Adverse Reaction:***

All noxious and unintended responses to a medicinal product related to any dose should be considered adverse reactions (ARs).

(The phrase “responses to a medicinal product” means that a causal relationship between a medicinal product and an AE is at least a reasonable possibility.)

***Unexpected Adverse Reaction:***

An unexpected AR is an AR, the nature or severity of which is not consistent with the applicable product information (e.g., Investigator's Brochure for an unapproved investigational medicinal product).

The following additional definitions are used by Sanofi Pasteur:

***Solicited Reaction:***

A solicited reaction is an event that is prelisted in the eCRF. The assessment of these AEs post-vaccination is mandatory. A solicited reaction is defined by a combination of:

- Symptom and
- Onset post-vaccination

Examples of solicited reactions include injection site pain between Day 0 and Day 7 post-vaccination, or headache between Day 0 and Day 7.

A solicited reaction is therefore an AR observed and reported under the conditions (symptom and onset) prelisted (i.e., solicited) in the eCRF and considered as related to vaccination.

***Unsolicited AE/AR:***

An unsolicited AE is an observed AE that does not fulfill the conditions prelisted in the eCRF in terms of diagnosis and/or onset post-vaccination. For example, if headache between Day 0 and

---

a Medical and scientific judgment should be exercised in deciding whether expedited reporting is appropriate in other situations, such as important medical events that may not be immediately life-threatening or result in death or hospitalization but may jeopardize the health of the subject or may require intervention to prevent one of the other outcomes listed in the definition above. These should also usually be considered serious. Examples of such events include allergic bronchospasm requiring intensive treatment in an emergency room or at home, blood dyscrasias or convulsions that do not result in inpatient hospitalization, the development of drug dependency or drug abuse, or new-onset diabetes or autoimmune disease.

Day 7 is a solicited reaction (i.e., prelisted in the eCRF), then a headache starting on Day 7 is a solicited reaction, whereas headache starting on Day 8 post-vaccination is an unsolicited AE.

An unsolicited non-serious AE is an unsolicited AE excluding SAEs.

***Injection Site Reaction:***

An injection site reactiona is an AR at and around the injection site. Injection site reactions are commonly inflammatory reactions.

***Systemic AE:***

Systemic AEs are all AEs that are not injection site reactions. They therefore include systemic manifestations such as headache, fever, as well as localized or topical manifestations that are not associated with the vaccination site (e.g., erythema that is localized but that is not at the injection site).

***Adverse Events of Special Interest:***

AEs of special interest are AEs that are considered by the Sponsor to be relevant for the monitoring of the safety profile of the investigational vaccine.

**4.3.1.2 Safety Endpoints**

The observational endpoints for the evaluation of safety are:

- 1) Occurrence, nature (Medical Dictionary for Regulatory Activities [MedDRA] preferred term [PT]), duration, intensity, and relationship to vaccination of any unsolicited systemic AEs reported in the 20 minutes after each vaccination.
- 2) Occurrence, time to onset, number of days of occurrence, intensity, action taken, and whether the reaction led to early termination from the study, of solicited injection site reactions (prelisted in the subject's diary card and eCRF) occurring between Day 0 and Day 7 after each vaccination.
- 3) Occurrence, time to onset, number of days of occurrence, intensity, action taken, and whether the reaction led to early termination from the study, of solicited systemic reactions (prelisted in the subject's diary card and eCRF) occurring between Day 0 and Day 7 after each vaccination.
- 4) Occurrence, nature (MedDRA PT), time to onset, duration, intensity, action taken, relationship to vaccination (for systemic AEs only), and whether the event led to early termination from the study, of unsolicited AEs between Visit 1 and Visit 2 for subjects receiving 1 dose or between Visit 1 and Visit 3 for subjects receiving 2 doses.
- 5) Occurrence, nature (MedDRA PT), time to onset, seriousness criteria, relationship to vaccination, outcome, and whether the SAE led to early termination from the study, of SAEs between Visit 1 and Visit 2 for subjects receiving 1 dose or between Visit 1 and Visit 3 for subjects receiving 2 doses.

---

a All injection site AEs are considered to be related to vaccination; therefore, all *injection site* AEs are *injection site reactions*.

Adverse events of special interest will be captured as SAEs. These include new onset of GBS, encephalitis/myelitis (including transverse myelitis), neuritis (including Bell's palsy, optic neuritis, and brachial neuritis), thrombocytopenia, vasculitis, convulsions (including febrile convulsions), and anaphylaxis or other hypersensitivity/allergic reactions between Visit 1 and Visit 2 for subjects receiving 1 dose, or between Visit 1 and Visit 3 for subjects receiving 2 doses.

#### 4.3.1.3 Safety Assessment Methods

See Section 9.3.1.3 of the protocol version 2.0, 13 June 2016.

### 4.3.2 Immunogenicity

The observational immunogenicity objective is presented in [Section 2.3.2](#).

#### 4.3.2.1 Immunogenicity Endpoints

Immunogenicity will be evaluated in a subset of approximately 1600 randomly selected subjects prior to vaccination on Day 0 (Visit 1) and at 28 (window, 28–35) days after the final vaccination using the HAI technique. For each influenza vaccine strain, HAI assay titers at pre-vaccination (Day 0) and at 28 (window, 28–35) days after the final vaccination will be determined in duplicate.

The derived endpoints are:

- Geometric means of HAI assay titers for individual subjects at pre-vaccination (Day 0) and at 28 (window, 28–35) days after the final vaccination.
- Ratios of individual post-final vaccination titers divided by individual pre-vaccination titers.
- Seroprotection: subjects with a titer  $\geq 40$  (1/dil) at pre-vaccination or at 28 (window, 28–35) days after the final vaccination.
- Seroconversion: subjects with either a pre-vaccination titer  $< 10$  (1/dil) and a post-vaccination titer  $\geq 40$  (1/dil), or a pre-vaccination titer  $\geq 10$  (1/dil) and a  $\geq 4$ -fold increase in post-vaccination titer at 28 (window, 28–35) days after the final vaccination.

#### 4.3.2.2 Immunogenicity Assessment Methods

The immunogenicity assessment methods are presented in [Section 4.2.2](#).

## 4.4 Derived Endpoints: Calculation and Derivation Methods

### 4.4.1 Safety

#### 4.4.1.1 Solicited Reactions

##### 4.4.1.1.1 Daily Intensity

All daily records for solicited reactions will be derived into daily intensity according to the following classification: None, Grade 1, Grade 2, Grade 3, or Missing.

For the derivation of daily intensities, the following sequential steps will be applied:

- 1) For solicited reactions (except fever/pyrexia) for which an Investigator records their presence as “No” and for which all daily records are missing, all daily intensities will be derived as None
- 2) For a temperature with partially missing data (MD) after the decimal point, the data will be analyzed by replacing “MD” with zero. For example, a “39.MD°C” daily temperature will be considered as “39.0°C” in the analysis
- 3) For non-measurable solicited reactions, daily intensities will correspond to daily records reported in the clinical database. For measurable solicited reactions, the daily measurements reported in the clinical database will be converted based upon the intensity scales defined in the protocol; this assumes a reaction that is too large to measure (non-measurable, “NM”) is Grade 3

Note: The maximum intensity during the ongoing period will be derived from the record of the maximum intensity/measurement after the end of the solicited period following the rule described above.

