##### 4.4.1.1.3 Presence

Presence will be derived from the maximum overall intensity during the period considered:

- None: No presence
- Grade 1, Grade 2, or Grade 3: Presence
- Missing: Missing presence

Subjects with at least 1 non-missing presence for a specific endpoint will be included in the analysis. Conversely, those with all missing presence will not be included in the analysis of the endpoint.

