### 5.1.3.1 Safety Analysis

The safety analysis will report the occurrence of solicited reactions and the incidence of unsolicited AEs between Visit 1 and Visit 2 (or between Visit 1 and Visit 3 for those subjects receiving 2 doses).

To avoid any under-estimation of the incidences, the number of subjects with documented safety will be used as denominator for the frequencies.

- For solicited reactions, the denominator will be the total number of subjects who have non-missing data for the endpoint considered
- For unsolicited AEs, the denominator will be the total number of subjects who were vaccinated at the dose analyzed.

The safety tables will be produced using a subject approach, i.e., number of subjects who experienced at least 1 safety event during a considered period.

The 2-sided 95% CIs for the percentages will be calculated using the exact binomial method (Clopper-Pearson method).

Additional safety tables, which will be based on analyses that exclude safety data from Site 009, will be presented in the CSR appendices. Specifically, these tables will be those that provide overall safety overviews/summaries and those that describe solicited reactions after any vaccination by maximum intensity.

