## 5.3 Handling of Missing Data and Outliers

### 5.3.1 Safety

No replacement of missing data will be done. All subjects with safety data and all safety data recorded in the eCRFs will be included in the safety analyses. No search for outliers will be performed.

In all subject listings, partial and missing data will be clearly indicated as missing.

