#### 5.3.1.3 Measurements

Missing measurements (for temperature or length) will remain missing and will not be imputed. Nevertheless, the following rule will be applied: If the measurement (temperature or length) is missing the value after the decimal point, the data will be analyzed by replacing “MD” with zero. For example, a “102.MD $^{\circ}\text{F}$ ” daily temperature will be considered as “102.0 $^{\circ}\text{F}$ ” during the analysis.

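### For the eight solicited reactions other than fever, a recorded No without daily entries is kept as a non-case, but a recorded Yes without daily entries has no rule and falls out, which can only lower each arm's any-grade rate

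*SAP*

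**What the plan says.** SAP 4.4.1.1.1 derives a daily intensity for each solicited reaction in sequential steps.

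- **Step 1** opens "For solicited reactions (except fever/pyrexia", closing the bracket there. It covers tenderness, erythema and swelling (Protocol Table 9.1) and vomiting, abnormal crying, drowsiness, lost appetite and irritability (Protocol Table 9.2): 3 + 5 = 8 reactions. It applies to reactions "for which an Investigator records their presence as “No” and for which all daily records are missing, all daily intensities will be derived as None".
- **Step 2** concerns temperatures with a missing decimal and is not relevant here.
- **Step 3** takes the grade from the daily data alone. For graded reactions, "For non-measurable solicited reactions, daily intensities will correspond to daily records reported in the clinical database". For measured reactions, "the daily measurements reported in the clinical database will be converted based upon the intensity scales defined in the protocol".

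SAP 5.3.1.3 adds: "Missing measurements (for temperature or length) will remain missing and will not be imputed". SAP 4.4.1.1.2 takes the maximum of the daily intensities, and 4.4.1.1.3 derives presence from that maximum. A child with at least one non-missing presence is analysed. "Conversely, those with all missing presence will not be included in the analysis of the endpoint".

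Two general statements stand beside these rules. SAP 5.1.3.1: "To avoid any under-estimation of the incidences, the number of subjects with documented safety will be used as denominator for the frequencies". SAP 5.3.1: "All subjects with safety data and all safety data recorded in the eCRFs will be included in the safety analyses".

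**The concern.** Among children with no daily entries for a reaction, whether the child is analysed depends on the answer recorded. A No is accepted and kept. A Yes is not used, and the child leaves the numerator and the denominator for that dose. Selection on the outcome has a known direction within each arm, and here it runs against the SAP's stated wish to avoid under-estimation.

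The situation can arise. Diary cards are collected 28 to 35 days after vaccination (Protocol 5.1.4), and gaps are clarified verbally with the family (Protocol 11.1 and 13.2). A parent may remember that there was swelling but not its size on each day. Such an event still meets the SAP's definition of a solicited reaction (4.3.1.1), which rests on symptom and onset, not on grade.

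At stake are the any-grade rates of the eight reactions. With fever, they describe how well 0.5 mL is tolerated against 0.25 mL, in a study meant to support a change to the Prescribing Information (Protocol 1.4).

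**Working it through.** The documents give no figure on this point, so there is nothing to reproduce. The check is a trace of the rules followed by arithmetic on assumed counts.

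**Trace, one dose, one reaction other than fever**

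| Presence field | Daily records | Maximum intensity | Presence | Analysed as |
|---|---|---|---|---|
| No | all missing | None (step 1) | No presence | non-case |
| Yes | all missing | Missing (no step applies) | Missing | excluded |
| Yes | at least one graded day | Grade 1 to 3 | Presence | case |

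**Direction.** Let n be the children with any usable record for the reaction, a those with a graded reaction, and y those with a recorded Yes but no daily entries.

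- Rate under the SAP: a/(n − y)
- Rate counting every recorded Yes: (a + y)/n
- Second minus first: y(n − a − y)/[n(n − y)]

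The last expression is never negative. It is zero only if y = 0 or if every child has the reaction.

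**Size, illustrated.** n = 1095 is the planned number per arm (SAP 3.2). The 20% rate (219 reactors) and the values of y are assumptions.

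| y | y as share of reactors | SAP rate | All Yes counted | Difference (points) |
|---|---|---|---|---|
| 5 | 5/219 = 2.3% | 214/1090 = 19.6% | 20.0% | −0.4 |
| 11 | 11/219 = 5.0% | 208/1084 = 19.2% | 20.0% | −0.8 |
| 22 | 22/219 = 10.0% | 197/1073 = 18.4% | 20.0% | −1.6 |

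For y = 11 the formula gives 11 × 876/(1095 × 1084) = 0.0081, which agrees with the table. At other assumed rates, also with y = 11: 55 recorded reactors give 44/1084 = 4.1% against 5.0%, and 548 give 537/1084 = 49.5% against 50.0%.

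**Any-dose summary.** A two-dose child with an ungraded Yes after one dose and None after the other has one non-missing presence, so the child stays in as a non-case. If all 11 children were of this kind, the rate would be 208/1095 = 19.0%, slightly lower than 19.2%. If the other dose has a graded reaction, the any-grade rate loses nothing.

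**The asymmetry fixes the direction.** Suppose children with a No and no daily records were dropped as well. With y = 11, dropping 55 of them gives 208/(1084 − 55) = 20.2%, and dropping 110 gives 208/(1084 − 110) = 21.4%. Either sign would then be possible.

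**Between arms.** With 219 recorded reactors in each arm, y = 5 in Group 1 and 22 in Group 2 gives 18.36% − 19.63% = −1.3 points for Group 2 minus Group 1. Reversing the counts gives +1.3. Equal counts give 0.

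**The case against.** The strongest reply is that the situation should be rare. Assessment of solicited reactions is mandatory (SAP 4.3.1.1). Sites interview the parent and try to resolve incomplete entries (Protocol 11.1), logic and consistency checks lead to queries (Protocol 11.2), and diary gaps are clarified verbally (Protocol 13.2). The same process may recover a daily grade, and the eCRF may not accept a Yes without daily values. This stands as an argument about size. It does not supply the missing rule.

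A second reply is that SAP 5.3.1.4 promises a missing class for intensity in the descriptive tables, which, read with 5.3.1, might let an ungraded reaction be shown. The table shells are in a separate file (SAP 6) that is not available here. But 5.3.1.4 does not say that such a child counts as having the reaction, and it does not override the exclusion in 4.4.1.1.3. At best a programmer would have to choose between the two.

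Several stronger readings are tempting but unsupported:

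- **Many children are lost.** Only blank daily records among reactors matter. Blank records with a No cause no bias, however common they are, and the documents give a frequency for neither group.
- **The rule favours 0.5 mL.** Both arms use the same diary process, and safety assessors are blinded (Protocol 6.4). Nothing suggests unequal counts, and the sign could go either way.
- **Reported rates are too low overall.** The direction applies to this rule's effect on each arm's any-grade rate. It says nothing about children with neither a presence answer nor daily data.
- **The trial's conclusion is at risk.** The Protocol Synopsis calls the observational safety analyses descriptive, with no hypothesis tested. Fever has its own derivation in SAP 4.1.2, where a No without readings is set to missing.

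**Conclusion.** The point holds as a gap with a known direction. As written, SAP 4.4.1.1.1 to 4.4.1.1.3 keep a recorded No without daily entries and lose a recorded Yes without them. Relative to counting every recorded Yes, this can only lower each arm's any-grade rate for the eight reactions, which is at odds with SAP 5.1.3.1 and 5.3.1. The outcome for Yes is not stated in words; it follows from reading the steps together.

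The size is unknown and probably small. The illustrated losses of 0.4 to 1.6 points at a 20% rate rest entirely on the assumed 5 to 22 children per arm; with none, there is no effect. No confirmatory result depends on it. The correction is still worth making, because it costs almost nothing and removes an exclusion that depends on the outcome.

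**What to change.** Add to SAP 4.4.1.1.1 and 4.4.1.1.3, for solicited reactions other than fever: where presence is recorded as Yes and all daily records are missing, presence is set to Presence and intensity to Missing. The child counts in the numerator and denominator for any intensity, after that dose and in the any-dose summary, and appears in the missing-intensity class of 5.3.1.4. Time of onset and number of days of occurrence stay missing, so no grade or date is imputed. Report the number of such children by arm for each reaction.

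The cost is one sentence in the SAP and a small programming change. Where such children exist, any-grade rates become slightly higher and the tables gain a missing-intensity row. If there are none, no result changes.

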##### 4.4.1.1.2 Maximum Overall Intensity

Maximum overall intensity will be derived from the daily intensities computed as described in [Section 4.4.1.1.1](#) and will be calculated as the maximum of the daily intensities during the period considered.

##### 4.4.1.1.3 Presence

Presence will be derived from the maximum overall intensity during the period considered:

- None: No presence
- Grade 1, Grade 2, or Grade 3: Presence
- Missing: Missing presence

Subjects with at least 1 non-missing presence for a specific endpoint will be included in the analysis. Conversely, those with all missing presence will not be included in the analysis of the endpoint.

#### 4.4.1.1.4 Time of Onset

Time of onset will be derived from the daily intensities computed as described in [Section 4.4.1.1.1](#). It will correspond to the first day with intensity of Grade 1, Grade 2, or Grade 3.

Note: If a reaction is not continuous (i.e., reaction occurs during 2 separate periods of time intervened by at least 1 daily intensity of Missing or None) then the time of onset is the first day of the first occurrence. For subjects who received 2 doses, the worst-case scenario will be used for the post-any dose summary (i.e., the smaller time of onset [latency] period will be used if present for both doses, or the available time of onset [latency] period will be used if present for either dose).

Note: Unsolicited non-serious AEs that occur before vaccination (i.e., those with a negative time of onset) will not be included in the analysis, but will be listed separately.

